6.4.4 Surgical complications during hospital stay

Using the safety set, the null hypothesis of true equality in the proportion of patients experiencing one or more episodes of each of the key complications (oesophagoenteric leak, conduit failure, chyle leak, pneumonia, GI bleeding requiring intervention) will be tested using a chi-square test.

For each patient the most severe impact of any complications during their initial hospital stay will be categorised using the Clavien-Dindo system(2), patients in the LAO and OO groups being compared using ordered logistic regression.

6.4.5 Post-operative pain

Using the full analysis set, the number responding, median, first and third quartile pain scores will be presented for LAO and OO groups at each of three days and six days. Medians and first and third quartiles will be presented. The null hypothesis of no true difference in pain at 6 days, comparing LAO and OO groups will be tested using the Mann-Whitney U test. Where patients have responded with a score between 0 and 10 rather than completing the visual analogue scale, the score will be converted by assuming that each point score = 10mm along the visual analogue scale.

6.4.6 Post-operative lung function

Using the full analysis set, for each of the three- and six-day assessments separately, FEV₁ and FVC as a percentage of the baseline measurement will be compared between the LAO and OO groups. Medians and first and third quartiles will be presented. The evidence against the null hypothesis of no difference in lung function between OO and LAO groups will be quantified using the Mann-Whitney U test.

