2.7 Sample size and justification

The theoretical advantage of LAO compared to OO for patients is improved short-term recovery with the long-term survival benefit of surgery maintained. Consequently, the primary endpoint is the QLQ C30 Physical Function sub-scale measured at three and six-weeks post-surgery and three months post-randomisation.

For simplicity, and to indicate the minimum statistical power that will be achieved for the comparison of recovery, we consider just the six-week assessment of physical function. The planned analysis, based on the three-week, six-week, and three-month assessments of patient-reported physical function (primary outcome), and the baseline assessment as a covariate, is likely to have greater power than indicated here.

We are assuming that having adjusted analyses for centre, there will be no further need to accommodate clustering of outcomes by surgeon. In fact, as a team of surgeons is involved in each case (in decision-making, in-hospital care, and often in theatre), it would be difficult to do in practice.

A recent review of patient reported outcomes has indicated that the minimum clinically important difference on the QLQ-C30 Physical Function Scale is 0.4 standard deviations (1). Allowance for 5% of patients allocated to LAO undergoing OO, and 10% of patients in each group being found during surgery to have more extensive disease, can be achieved by reducing the effect size to be detected to 0.34 standard deviations. In this situation 182 patients in each group (364 patients in total) will allow a true treatment effect (LAO versus OO) of 0.4 standard deviations to be detected with 90% power at the 5% significance level, when up to 15% of patients are not able to follow their allocated procedure.

Further allowing for up to 10% missing outcome data, e.g. due to the patient being too sick, increases the target sample size to $364/0.9 = 406$ patients in total. Hence our sample size target for the definitive ROMIO trial is 203 patients allocated to LAO and 203 patients allocated to OO.

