3.4 Study centre effects

Variation between centres will be accommodated in each analysis by including dummy variables, distinguishing each centre (Bristol and Bath, plus Salford and South Manchester will be combined) in the regression model. There is no plan to investigate variation in the treatment effect by study centre.

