6.3 Primary analysis

The null hypothesis being addressed by the primary analysis is that, in truth, physical functioning in the three months following randomisation, measured with the physical function scale of the QLQ-C30, is identical whether access for a patient’s oesophagectomy was achieved with LAO or OO.

Using the full analysis set, the following analysis will be conducted separately for feasibility and full trial patients:

The relative effectiveness of the two approaches will be quantified as a difference in mean response on the physical function scale of the QLQ-C30 (LAO mean – OO mean), amongst patients in the full analysis set, using patients’ available measures from the three-week and six-week post-surgery, and the three-month post-randomisation assessments. The difference in mean response will be presented with its 95% confidence interval, and p-value.

The difference in means will be estimated in a mixed effects linear regression model with patient response at three-week (y_{i1}) and six-week (y_{i2}) post-surgery, and three-month (y_{i3}) post-randomisation as the outcome variables (i.e. between one and three outcome measurements per patient), and covariates: treatment allocation ($x_{1i}=1$: LAO; $x_{1i}=0$: OO), baseline physical function (x_{2i}), dummy variables distinguishing centres ($x_{3ki}=0,1$; $k=1,\dots,K$ indexing the centres), two dummy variables distinguishing assessment points ($x_{4ti}=0,1$; $t=1,2,3$), and a dummy variable distinguishing patients who underwent neoadjuvant treatment or not ($x_{5i}=1$: underwent neoadjuvant treatment; $x_{5i}=0$: no neoadjuvant treatment). Finally a dummy variable distinguishing those participant without a baseline assessment of outcome ($x_{6i}=1$: no baseline assessment; $x_{6i}=0$: baseline assessment available). A normally distributed random effect will accommodate the correlation between each patient’s responses: $z_i \sim N(0, \sigma_z)$. A normal distribution is assumed for the residual errors: $e_i \sim N(0, \sigma_e)$. The coefficient for the treatment allocation covariate (β_1) is the intention to treat estimate of treatment effectiveness, comparing LAO to OO. In statistical notation:

$$y_{it} = \beta_0 + \beta_1 x_{1i} + \beta_2 x_{2i} + \sum_{k=1}^K \beta_{3k} x_{3ki} + \sum_{t=1}^3 \beta_{4t} x_{4ti} + \beta_5 x_{5i} + \beta_6 x_{6i} + z_i + e_i$$

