6.4 Secondary analyses

6.4.1 Patient reported outcome questionnaires

Using the full analysis set, the primary analysis plan will be adapted to the analysis of each of the other scales from patient reported outcomes. For these secondary analyses, it may be necessary to present the pooled estimate (combining feasibility and full trial estimates) in the paper, with the feasibility and full trial specific estimates presented in supplementary material. Where the feasibility and full trial estimates are noticeably different to the extent of supporting different conclusions, this will be highlighted.

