Pneumonia / chest infection			
Delayed gastric emptying			
GI bleeding requiring intervention or transfusion			
Acute abdominal wall dehiscence/hernia			
Further intervention, n (%)			
Reoperation during index hospitalisation			
Return to ITU/HDU during index hospitalisation			
Within three months of randomisation			

Table 4. Peri- and post-surgical measures

	OO (n=)	LAO (n=)	p-value
30-day post-operative mortality, n (%)			
90-day post-operative mortality, n (%)			
Median total hospital stay in days (Q1, Q3) ¹			
Median post-surgical hospital stay in days (Q1, Q3) ¹			
Median total lymph nodes retrieved (Q1, Q3) ¹			
Median lymph nodes with tumour (Q1, Q3) ¹			
Resection margins, n (%)²			
R0			
R1			
R2			
pStage, n (%)²			
0			
I or II			
III			
IV			
No residual tumour or lymph-node metastasis			
Median FEV₁, as a percentage of pre-surgery (Q1 Q3), n			
Three days post-surgery ¹			
Six days post-surgery ¹			
Median FVC, as a percentage of pre-surgery (Q1 Q3), n			
Three days post-surgery ¹			
Six days post-surgery ¹			
Median pain (Q1, Q3), n; 0 is no pain, 100 is worst possible pain.			
Three days post-surgery ¹			
Six days post-surgery ¹			

1. p-value based on Mann-Whitney U statistic. Note that Q1 and Q3 are the first and third quartiles

2. p-value based on ordered logistic regression

Supplementary Table 1. Post-surgery treatment complications in those undergoing their allocated surgery [specific complications will be detailed if they occur in one or more patients – those listed here are examples only]

	OO (n=)	LAO (n=)
Pulmonary complications, n (%)		
Respiratory failure requiring intubation		
Acute respiratory distress syndrome		
Cardiac complications, n (%)		
Dysrhythmia atrial requiring treatment		
Dysrhythmia ventricular requiring treatment		
Urological complications, n (%)		
Acute renal insufficiency		
Gastrointestinal complications, n (%)		
Anastomotic stricture requiring endoscopic intervention		
Thromboembolic complications, n (%)		
Pulmonary embolism		
Neurological / psychiatric complications, n (%)		
Other neurological injury		
Post-operative infections, n (%)		
Wound infection requiring opening wound or antibiotics		
Post-operative wound / diaphragm complications, n (%)		
Acute abdominal wall dehiscence / hernia		
Other post-operative complications, n (%)		
Multiple organ dysfunction syndrome		

Supplementary Table 2. Cohort stratified and pre-specified subgroup analyses

	OO (n=)	LAO (n=)
Main study cohort		

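### Baseline FEV1 and FVC serve only as the denominator of a percentage tested by an unadjusted Mann-Whitney test; a pre-specified baseline-adjusted model would usually be more efficient and would give an estimate with a confidence interval

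*SAP*

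**What the plan says.** SAP section 6.4.6 takes the day 3 and day 6 assessments separately. At each, FEV1 and FVC "as a percentage of the baseline measurement will be compared between the LAO and OO groups". Medians and quartiles are shown, and "The evidence against the null hypothesis of no difference in lung function between OO and LAO groups will be quantified using the Mann-Whitney U test". Footnote 1 of Table 4 (section 8), marked on the FEV1 and FVC rows, agrees: "p-value based on Mann-Whitney U statistic". Table 4 has a column for each group and a p-value column, but none for a treatment difference or its confidence interval.

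The SAP treats baseline differently elsewhere. The primary model in section 6.3 includes "baseline physical function (x_{2i}), dummy variables distinguishing centres" and a neoadjuvant term. Section 6.4.1 extends it: "the primary analysis plan will be adapted to the analysis of each of the other scales from patient reported outcomes". Section 3.4 states as a general rule: "Variation between centres will be accommodated in each analysis by including dummy variables".

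**The concern.** The trial already collects a baseline for each spirometry measure, and baseline is usually the strongest single predictor of the later value. Dividing by it uses that information with a fixed weight. On the log scale, the percentage of baseline is the post-operative value minus 1 times the baseline value, whatever the true slope. If the true slope is below 1, the percentage over-corrects: it keeps baseline noise, and patients who start low tend to show a better percentage.

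Three things are at stake:

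- power for an objective early measure of respiratory recovery;
- part of the protection against chance baseline imbalance;
- an interpretable estimate with its uncertainty, where only a p-value is planned.

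The planned analysis also sits awkwardly with section 3.4, because a plain Mann-Whitney test cannot include centre dummies.

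**Working it through.** **The plan's own figure.** Section 2.7 powers physical function only: 0.34 SD, "detected with 90% power at the 5% significance level". Two-sided, n = 2 × ((1.960 + 1.282)/0.34)² = 181.8, so 182 per group. Allowing for 10% missing data, 182/0.9 = 202.2, so 203 per group and 406 in total. This reproduces. The SAP states no power, effect size, SD or correlation for lung function.

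**Assumed inputs.** r is the correlation of log baseline with log post-operative value, 0.4 to 0.8. λ is the post-operative log SD divided by the baseline log SD, 0.8 to 1.4. There are 182 per group, and the effect is set so that Mann-Whitney on the percentage has 80% power.

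**Formulas, with baseline log SD set to 1.**

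- Variance of the log percentage: λ² + 1 − 2rλ.
- Residual variance after baseline adjustment: λ²(1 − r²).
- Adjusted over ratio at λ = 1: (1 − r²)/(2 − 2r) = (1 + r)/2.
- The true log-log slope is rλ. The ratio is fully efficient only when rλ = 1.
- Mann-Whitney efficiency relative to a normal-theory test on normal data: 3/π.

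The adjusted analysis then has power Φ(2.802 × √(π/3) × √(ratio variance/adjusted variance) − 1.960). At λ = 1 and r = 0.5 the variance ratio is 0.75, so the power is Φ(2.802 × 1.023 × 1.155 − 1.960) = Φ(1.35) ≈ 91%, a gain of about 11 points.

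| λ | r = 0.4 | 0.5 | 0.6 | 0.7 | 0.8 |
|---|---|---|---|---|---|
| 0.8 | 17.4 | 16.7 | 15.9 | 15.1 | 14.8 |
| 1.0 | 12.9 | 11.2 | 9.4 | 7.5 | 5.6 |
| 1.2 | 8.7 | 6.7 | 4.8 | 3.1 | 1.9 |
| 1.4 | 5.8 | 4.0 | 2.5 | 1.8 | 2.5 |

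Entries are gains in power points. About 1.8 points of each entry come from replacing a rank test by a normal-theory test on normal data. The rest comes from estimating the slope. At λ = 1.4 and r = 0.7 the slope is 0.98, so the ratio itself costs nothing. Simulation with normal errors agrees: at λ = 1 the gains were 10.5, 7.8 and 5.9 points for r = 0.5, 0.7 and 0.8, and the smallest gains at λ = 1.4 were about 1 to 2 points.

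**Heavy tails.** The simulation was repeated with t errors on 5 degrees of freedom and the same variance (4,000 runs per setting). Power, Mann-Whitney on the percentage against linear log-scale adjustment:

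| λ | r | Mann-Whitney | Adjusted |
|---|---|---|---|
| 1.0 | 0.5 | 83% | 90% |
| 1.0 | 0.7 | 85% | 86% |
| 1.0 | 0.8 | 87% | 84% |
| 1.2 | 0.7 | 86% | 81% |
| 1.4 | 0.7 | 87% | 79% |

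The gain shrinks and can reverse.

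**Imbalance at λ = 1.** A baseline difference of 0.1 SD, about one standard error at 182 per group (√(2/182) = 0.105), shifts the ratio comparison by 0.1 × (1 − r) SD. The standard error of that comparison is √(2 − 2r) × 0.105 SD, so the shift is 0.52 standard errors at r = 0.4 and 0.30 at r = 0.8.

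**The case against.** The strongest reply is that nothing is wrong with the planned test. Mann-Whitney on percentage of baseline is a valid randomised comparison that controls type I error. It does use baseline, it is robust to outliers, and lung function is a secondary outcome with no stated power. All of this stands, and the heavy-tail results show that the robustness is worth something.

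Section 6.4.6 also matches its neighbours: post-operative pain (6.4.5) and length of stay (6.4.7) are tested the same way. So a reader should not infer that every patient-reported scale in the SAP is baseline-adjusted. That holds for the questionnaire scales under 6.4.1, not for pain. Section 3.4 could also be read as applying only where a regression model is fitted, although its wording covers each analysis.

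Three stronger readings are tempting, and the SAP does not support them:

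- **A definite loss of 5 to 13 power points.** That is the equal-SD case with normal errors, and the SAP supplies neither an SD nor a correlation.
- **No protection against baseline imbalance.** At equal SDs the imbalance left over is proportional to 1 − r under the ratio and to r with no adjustment, so the ratio does better than no adjustment once r exceeds 0.5.
- **A bias that always favours the arm with poorer starting lung function.** This holds only when the log-log slope is below 1. At λ = 1.4 and r = 0.8 the slope is 1.12 and the direction reverses. Averaged over randomisations, a true null is not biased.

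**Conclusion.** The concern holds as a cheap improvement, not as an error in the test. Section 6.4.6 and Table 4 use baseline spirometry only as a divisor, plan no estimate or confidence interval, and leave out the centre terms of section 3.4.

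Under normal log-scale errors, estimating the slope is never less efficient than fixing it at 1. The likely gain is about 5 to 13 power points at equal SDs, about 1 to 9 with a post-operative SD 20 to 40% larger, and about 15 to 17 with one 20% smaller. All of these rest on assumed correlations of 0.4 to 0.8. With heavy-tailed errors a linear model may gain nothing or lose several points, so a robust companion analysis is needed. Severity is low: the outcome is secondary, the planned test is valid, and the primary conclusion is unaffected.

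**What to change.** In section 6.4.6:

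1. Keep the medians and quartiles of percentage of baseline as description.
2. Base the comparison at each of days 3 and 6 on a linear regression of log(FEV1), and likewise log(FVC), on allocation, log(baseline value), centre and neoadjuvant treatment. Report the LAO/OO ratio of geometric means with its 95% confidence interval.
3. Pre-specify one robust check: either proportional odds regression with the same covariates, or the currently planned Mann-Whitney test as a sensitivity analysis. Do not leave the choice of method until the residuals have been seen.
4. Amend footnote 1 of Table 4 for the FEV1 and FVC rows, and add the estimate and interval.

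The cost is SAP wording and a few lines of code, with no new data. The downsides are that a log-scale model is assumed and that the p-value no longer comes from the same statistic as the displayed medians.

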6.4.7 Length of hospital stay

Using the full analysis set, total and post-surgical inpatient stay will be compared between LAO and OO groups. Medians and first and third quartiles will be presented. The evidence against the null hypothesis of no difference in hospital stay between OO and LAO groups will be quantified using the Mann-Whitney U test.

6.4.8 Overall and recurrence-free survival to two years.

A Kaplan-Meier plot will present survival over time in the OO and LAO groups. Kaplan-Meier estimates of survival, with 95% confidence intervals will be presented for survival in each of the OO and LAO groups at the following time points: 30 days, 90 days, 24 months.

Using the full analysis set, the hazard ratio comparing those allocated to LAO to those allocated to OO in terms of all-cause mortality, and recurrence-free survival will be estimated using proportional hazards models with time to event as the outcome measure and covariates: allocated surgery, dummy variables distinguishing the centres, and a dummy variable distinguishing those patients who underwent neoadjuvant treatment, and those who did not. Marked evidence against the proportional hazards assumption will be investigated in a test based on Schoenfeld residuals(10). Estimated hazard ratios will be presented with 95% confidence intervals.

This analysis is aimed at ruling out a large difference in survival between LAO and OO, as the benefit of LAO is expected to be limited to faster recovery in the initial months post-surgery. Our equivalence bound is a 7% difference in mortality risk, such that the 95% confidence interval for the risk difference at 24 months post-randomisation is entirely within the range -7% to +7%.

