3. GENERAL ANALYSIS CONSIDERATIONS

3.1 Analysis populations

Each of the following will include participants of the feasibility and main trials, according to the availability of data.

The primary effectiveness analysis will include data from the **“full analysis set”**; all randomised participants **in the groups to which they were allocated** (i.e. according to the intention-to-treat principle) who provide at least one of the three post-treatment assessments of physical function contributing to the primary outcome.

The **“safety set”** will include all randomised participants for whom there was an attempt to complete a study procedure (OO or LAO). This does not include patients for whom curative surgery did not proceed (e.g. due to the discovery of more advanced disease). The safety set does include participants who underwent a study procedure which was not that allocated, and participants who needed to convert from LAO to OO due to clinical reasons. This is the analysis population that will be used in the reporting of complications and adverse events. The groups to be compared will be defined by the study procedure **first initiated**, e.g. participants will be retained in the LAO group, even if they subsequently needed to convert to OO.

The **“per protocol set”** will include all randomised participants, **in their allocated groups**, for whom the allocated surgery was completed. Analyses of blinding, and surgical quality will use data from these participants.

Within the above three sets, about 120 feasibility phase patients, allocated to OO or LAO and with the necessary data, will be distinguished from those patients allocated to OO and LAO in the main study. In general, estimates of effectiveness will be stratified by feasibility and main study, and presented with a third pooled estimate using data from the two study phases.

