3.3 Procedures for missing data

The primary effectiveness analysis will be based upon those randomised participants who provide at least one of the three post-treatment assessments of physical function contributing to the primary outcome.

The five QLQ-C30 items contributing to the physical function scale are as follows:

1. Do you have any trouble doing strenuous activities, like carrying a heavy shopping bag or a suitcase?
2. Do you have any trouble taking a long walk?
3. Do you have any trouble taking a short walk outside of the house?

4. Do you need to stay in bed or a chair during the day?
5. Do you need help with eating, dressing, washing yourself or using the toilet?

A patient will be considered to have completed the physical function scale and to have a score of zero (lowest level of physical functioning), if their reason for not having a physical function score is recorded as due to being in intensive care or having died prior to the questionnaire being due. This is a reasonable assumption about responses to the above five questions in those circumstances and is to prevent these values being implicitly imputed by the statistical model upon which the analysis is based. This approach will only be used for the physical function and role function scales, where the assumption of a zero value can be justified; the number of values imputed in this way will be reported by treatment group. The two items contributing to role function are:

6. Were you limited in doing either your work or other daily activities?
7. Were you limited in pursuing your hobbies or other leisure time activities?

Participants missing their baseline assessment of a patient reported outcome will be included in the analysis by (i) imputing the overall mean for the corresponding observed baseline measurements, (ii) including an indicator variable as a covariate with values 0 if the individual has provided a baseline measure, and value 1 if not. This approach has been shown to give unbiased estimates in a randomised trial, and to avoid the loss of power that a complete case analysis will cause(8).

When single items are missing from any of the patient reported outcomes, these will be addressed using the accepted guidelines where available.

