5.3 Study completion

All patients will be followed up for 24 months post-randomisation, for vital status, and through completion of PROs. If possible within the study follow-up period, patients can be followed up for 36 months.

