6.2 Summary of primary and secondary outcomes

For patients in the full analysis set, the number of patients providing data, mean, and standard deviation will be presented, by allocated group, for the time points used in the analysis of the primary outcome: baseline, three and six-weeks post-surgery, and three months post-randomisation. The primary outcome is based on the physical function scale of the QLQ-C30, a continuous measure with high scores indicating better physical function.

With regards to secondary outcomes, the same statistics will be presented for other scales derived from patient reported outcomes:

For function scales derived from the QLQ C-30 (role, emotional, cognitive, social), and global health status, high scores indicate high functioning / good quality of life.

For symptom scales derived from the QLQ C-30 (fatigue, nausea and vomiting, pain, dyspnoea, insomnia, appetite loss, constipation, diarrhoea, financial difficulties), high scores indicate greater symptom burden.

For the function scale derived from the QLQ-OES18 (dysphagia), a high score indicates good functioning.

For the symptom scales and items derived from the QLQ-OES18 (eating, reflux, pain, trouble swallowing saliva, choked when swallowing, dry mouth, trouble with taste, trouble with coughing, trouble talking), a high score indicates a high symptom burden.

For the five scales derived from the MFI-20 (general fatigue, physical fatigue, reduced activity, reduced motivation, mental fatigue) a high score indicates greater fatigue.

For the full analysis set, the occurrence of deaths, and of disease recurrence over a two-year follow-up period will each be presented for the LAO and OO groups as a Kaplan-Meier survival curves. Point estimates from these survival curves will be presented at 30 days and 90 days to allow comparison with National Audit Data.

For the safety set, the occurrence for each patient of one or more complications in each of the following key categories, both up to hospital discharge, and separately for the remainder of the 24-month follow-up, will be tabulated for the LAO and OO groups: oesophagoenteric leak and conduit necrosis/failure (patients experiencing each and both of these will be reported), chyle leak, pneumonia, gastrointestinal bleeding requiring intervention or transfusion. The number of patients requiring readmission to ITU/HDU will also be presented.

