Pre-randomisation mean (SD) n		
Three-week post-surgery mean (SD) n		
Six-week post-surgery mean (SD) n		
Three-month post-randomisation mean (SD) n		
Treatment effect (95% confidence interval)		
Feasibility study cohort		
Pre-randomisation mean (SD) n		
Three-week post-surgery mean (SD) n		
Six-week post-surgery mean (SD) n		
Three-month post-randomisation mean (SD) n		
Treatment effect (95% confidence interval)		
Neoadjuvant treatment		
Treatment effect (95% confidence interval)		
No neoadjuvant treatment		
Treatment effect (95% confidence interval)		
	Interaction p-value:	
BMI at or above the median		
Treatment effect (95% confidence interval)		
BMI below the median		
Treatment effect (95% confidence interval)		
	Interaction p-value:	
POSSUM Physiology at or above the median		
Treatment effect (95% confidence interval)		
POSSUM Physiology below the median		
Treatment effect (95% confidence interval)		
	Interaction p-value:	

Figure 1: CONSORT Flow chart

[figure not shown]

Table A. Survival and recurrence-free survival

	OO (n=)	LAO (n=)
Survival over 24 months post-randomisation		
Person-years of follow-up per group over 24 months		
Number of events over 24 months		
Survival at 24 months (95% confidence interval)		
Survival over full follow-up period		
Total person-years of follow-up per group		
Number of events		
Hazard ratio (95% confidence interval) p-value		
Recurrence-free survival over 24 months post-randomisation		
Person-years of follow-up per group over 24 months		
Number of events over 24 months		
Survival at 24 months (95% confidence interval)		
Recurrence-free survival over full follow-up period		
Total person-years of follow-up per group		
Number of events		
Hazard ratio (95% confidence interval) p-value		

Figure A: Mean QLQ-C30 Function sub-scale scores over two years of follow-up in patients allocated to LAO and OO. High scores indicate good function

Figure B: Mean QLQ-C30 Symptom sub-scale scores over two years of follow-up in patients allocated to LAO and OO. High scores indicate severe symptoms

Figure C: Mean QLQ-OES18 Function and Symptom sub-scale scores over two years of follow-up in patients allocated to LAO and OO. A high score indicates good swallowing function, and high symptom burden on the other measures

Figure D: Mean MFI-20 sub-scale scores over two years of follow-up in patients allocated to LAO and OO. High scores indicate greater fatigue

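### Survival, hospital stay, pain and lung function are analysed in a set defined by having a physical-function score, and the time origin of the survival curves is not stated

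*SAP*

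**What the plan says.** **Analysis set.** Section 3.1 defines the full analysis set as randomised participants, in their allocated groups, "who provide at least one of the three post-treatment assessments of physical function contributing to the primary outcome". Section 3.3 adds that the physical-function scale counts as completed, with a score of zero, when the recorded reason for a missing score is intensive care or "having died prior to the questionnaire being due".

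**Where the set is used.** Section 6.2 uses it for the Kaplan-Meier curves of death and recurrence. Section 6.4.8 uses it for the hazard ratios: "Using the full analysis set, the hazard ratio comparing those allocated to LAO to those allocated to OO in terms of all-cause mortality". Sections 6.4.5, 6.4.6 and 6.4.7 use it for pain, lung function and hospital stay.

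**What is collected.** Section 5.3 states: "All patients will be followed up for 24 months post-randomisation, for vital status". Completion of questionnaires is listed there as a separate item.

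**Time origin.** Section 6.2 says of the survival curves: "Point estimates from these survival curves will be presented at 30 days and 90 days to allow comparison with National Audit Data". Section 6.4.8 puts the equivalence bound of 7 percentage points at 24 months after randomisation, and Table A is headed "Survival over 24 months post-randomisation". Table 4 has a row "30-day post-operative mortality, n" (%) and a matching 90-day row. Neither 6.2 nor 6.4.8 says when the clock starts.

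**The concern.** A mortality comparison needs vital status, and the plan seeks it for every randomised patient. Requiring a physical-function score as well drops patients whose survival is known. The requirement is a post-randomisation event tied to outcome, because section 3.3 treats death differently from other reasons for having no score. Section 3.1 describes the set as intention-to-treat. That describes the grouping, but it does not bring back the patients left out.

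Those patients may well differ in prognosis. Section 2.7 attributes some missing data to patients being too sick, and allows for 10% of each group being found at surgery to have more extensive disease. If exclusion also differs between arms, the survival comparison can shift.

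Pain and spirometry at days three and six, and hospital stay, do not depend on the later questionnaire either. A patient with those measurements and no later score is left out for no stated reason.

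On time origin, a 30-day point counted from randomisation covers fewer than 30 post-operative days. It would not be the quantity in Table 4, nor a like-for-like figure if the audit counts from surgery.

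**Working it through.** **The plan's own figures.** The SAP gives no sample size or power for survival. Its primary-outcome size reproduces: 2 × (1.960 + 1.282)² / 0.34² = 181.8, so 182 per arm. 182/0.9 = 202.2, so 203 per arm and 406 in total. The 10% missing-data allowance is 0.10 × 406, or about 41 patients. It accompanies a calculation on the six-week assessment alone. Leaving the full analysis set requires all three scores to be missing, so 10% is an upper guide.

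**Who is in the set.**
- If the section 3.3 rule confers membership, patients recorded as dead before an assessment was due are in, and so are those recorded as in intensive care. Other patients alive at three months with no score are out.
- If it does not, patients who die before giving any score are out, and early mortality is understated.
- Membership depends on outcome under both readings.

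**Early mortality, first reading.** Let p be true early mortality and m the fraction of all randomised patients left out, all alive at that point. Mortality in the set is p/(1 − m). The values of p are assumptions.

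| p | m = 5% | m = 10% |
|---|---|---|
| 2% | 2.1% | 2.2% |
| 4% | 4.2% | 4.4% |
| 6% | 6.3% | 6.7% |

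**24-month mortality, first reading.** Let P be true mortality, the same in both arms, with 4% early deaths. Later mortality among early survivors is q = (P − 0.04)/0.96. Those left out have later mortality r × q. Mortality in the set is (P − m × r × q)/(1 − m). Assumed ranges: P from 25% to 45%, r from 0.5 to 1.5.

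Example with P = 45%, r = 0.5: q = 0.427 and r × q = 0.2135.
- LAO, m = 5%: (0.45 − 0.0107)/0.95 = 46.2%.
- OO, m = 15%: (0.45 − 0.0320)/0.85 = 49.2%.
- Spurious difference, LAO minus OO: -2.9 points.

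| P | r | 5% v 15% left out | 2% v 10% left out |
|---|---|---|---|
| 25% | 0.5 | -1.7 | -1.3 |
| 25% | 1.5 | +1.0 | +0.7 |
| 35% | 0.5 | -2.3 | -1.7 |
| 35% | 1.5 | +1.7 | +1.2 |
| 45% | 0.5 | -2.9 | -2.1 |
| 45% | 1.5 | +2.4 | +1.7 |

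With r = 1 and unequal exclusion, the shift is only -0.2 to -0.4 points. With equal exclusion (5% or 10% in both arms) and equal prognosis of those excluded, it is zero.

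**Time origin.** If the curve starts at randomisation and surgery follows after a lag, the post-operative day reached is the stated day minus the lag. Section 2.6 gives two weeks as a target limit; the other lags are assumptions.

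| Lag | Day 30 | Day 90 |
|---|---|---|
| 7 days | 23 | 83 |
| 14 days | 16 | 76 |
| 28 days | 2 | 62 |

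**The case against.** The strongest reply is that little is lost. A patient must miss all three assessments to leave the set, and the acceptance windows in section 3.5 run without a gap from day 10 to day 111. Few patients may be affected, and 15% in one arm exceeds the plan's own allowance. The larger shifts above need unequal exclusion and a different prognosis together. Only secondary outcomes are involved, and section 6.6 already repeats the six-day pain analysis in the per protocol set. All of this stands as a limit on size. It gives no reason to discard known vital status, and the per protocol set is narrower still.

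A reader might infer that the set keeps every early death and removes only survivors, so that the bias has one direction. The documents do not support that. The zero-score rule depends on a recorded reason, covers only deaths before an assessment was due, also keeps some living intensive-care patients, and may not confer membership at all. Patients left out at three months may die later, so the 24-month shift can go either way.

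A reader might also infer that selection could produce a false equivalence claim. Under the rates assumed here it could not. With P = 35% and 203 per arm, the half-width of the 95% interval is 1.96 × √(2 × 0.35 × 0.65/203) = 9.3 points (8.4 at P = 25%, 9.7 at 45%). It could not lie within ±7 points in either set.

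On time origin, randomisation is an inference from the 24-month wording, though a strong one. Table 4 already plans post-operative mortality, and nothing says that its rows come from the curve. What remains is an unstated origin and two sets of 30- and 90-day figures that may not agree. The statement that a 30-day point misses about half of post-operative deaths would need a full 14-day lag and evenly spread deaths, and the SAP gives neither.

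**Conclusion.** The plan is wrong as written on the analysis set. Survival, hospital stay, pain and lung function are restricted by a post-randomisation condition that they do not need and that depends on outcome. The bias is probably modest: early mortality is inflated by at most about 1/(1 − m), a factor of 1.11 at 10%. The 24-month risk difference shifts by between about -2.9 and +2.4 points under the assumed 5% against 15% exclusion, and not at all if exclusion and prognosis are equal across arms. Every mortality rate, exclusion rate and prognosis ratio here is an assumption, and no size is estimated for pain, lung function or hospital stay.

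The time origin is a secondary point of clarification. Both points should be fixed, but they affect secondary outcomes only and give no ground to question the primary analysis.

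**What to change.** 1. Add to section 3.1 a set of all patients randomised to OO or LAO, as allocated. Name it in 6.2 and 6.4.8 for overall and recurrence-free survival, and in 6.4.5 to 6.4.7 for pain, lung function and hospital stay wherever those were measured.
2. Keep the full analysis set for the questionnaire outcomes, and say in 3.1 whether a zero assigned under 3.3 counts as providing an assessment.
3. State in 6.2 and 6.4.8 that time zero is randomisation for the 24-month estimates and the hazard ratios.
4. Take the 30- and 90-day figures for audit comparison from the date of surgery, in a stated operated population, and use the same definition for Table 4. The definition should say how abandoned procedures are handled, since 3.1 separates attempted, completed and abandoned surgery.

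The cost is SAP wording. Vital status, hospital stay, pain and spirometry are already planned data. The step that needs thought is the definition of the operated population.
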